2.2.1 Potential risks of Lenvatinib

Oral lenvatinib had a manageable safety and tolerability profile in clinical trials. In patients with RAI-refractory differentiated thyroid cancer participating in SELECT, treatment-related adverse events (TRAES) of any grade occurred in 97.3 % of lenvatinib recipients and 59.5 % of placebo recipients, with TRAEs of grade 3 or higher occurring in 75.9 and 9.9 % of patients as mentioned by Schlumberger et al. In this study, Serious TRAEs occurred in 30.3 and 6.1 % of lenvatinib and placebo recipients. Treatment-emergent adverse events that lead to death occurred in 7.7 % of lenvatinib recipients and 4.6 % of placebo recipients, with 2.3 % of those occurring in the lenvatinib group considered to be treatment-related.

The most common (incidence ≥ 30 %) TRAEs of any grade occurring in lenvatinib recipients were hypertension (67.8 vs. 9.2 % in the placebo group), diarrhea (59.4 vs. 8.4 %), fatigue or asthenia (59.0 vs. 27.5 %), decreased appetite (50.2 vs. 11.5 %), decreased bodyweight (46.4 vs. 9.2 %), nausea (41.0 vs. 13.7 %), stomatitis (35.6 vs. 3.8 %), palmar-plantar erythrodysesthesia syndrome (31.8 vs. 8.0 %) and proteinuria (31.0 vs. 1.5 %).

TRAEs led to discontinuation of the study drug in 14.2 % of lenvatinib recipients and 2.3 % of placebo recipients, with the most frequent of these being asthenia and hypertension (each of which occurred in 1.1 % of lenvatinib recipients). Dosage reductions (67.8 vs. 4.6 %) or interruptions (82.4 vs. 18.3 %) occurred more frequently in the lenvatinib than in the placebo group. The most common adverse effects

associated with dosage discontinuations or interruptions of lenvatinib were diarrhea (22.6 %), hypertension (19.9 %), proteinuria (18.8 %) and decreased appetite (18.0 %).

TRAEs that occurred in clinical trials and for which there is a warning/precaution in US manufacturer's prescribing information were hypertension, cardiac dysfunction (decreased left or right ventricular function, cardiac failure or pulmonary oedema), arterial thromboembolic events, hepatotoxicity, proteinuria, renal failure and impairment, gastrointestinal perforation and fistula formation (incidence in SELECT: 2 % in the lenvatinib group vs. 0.8 % in the placebo group), QT interval prolongation, hypocalcemia, reversible posterior leucoencephalopathy syndrome (three cases across clinical studies; $n = 1108$ lenvatinib recipients), haemorrhagic events and impairment of thyroid stimulating hormone (TSH) suppression.

In SELECT, the incidences of these adverse events that were of grade 3 or higher in the lenvatinib and placebo groups were: hypertension (~44 vs. 4 %), cardiac dysfunction (2 vs. 0 %), arterial thromboembolic events (3 vs. 1 %), hepatotoxicity (4 vs. 0 % for an increase in alanine aminotransferase level; 5 vs. 0 % for an increase in aspartate aminotransferase level), proteinuria (11 vs. 0 %), renal failure or impairment (3 vs. 1 %), QT interval prolongation (2 vs. 0 %), hypocalcaemia (9 vs. 2 %) and haemorrhagic events (2 vs. 3 %). In patients who had normal TSH levels (≤ 0.5 mU/mL) at baseline in SELECT, 57 % of lenvatinib recipients and 14 % of placebo recipients had elevations in TSH level of >0.5 mU/mL.²⁷

2.3 Rationale for combining Lenvatinib and Eribulin

Lenvatinib (LEN) is an oral tyrosine kinase inhibitor of the VEGFR1-3, FGFR1-4, PDGFR β , RET, and KIT signaling networks[1]. It has shown activity in many solid tumors, such as NSCLC and thyroid cancer. Data on xenograft models have shown activity of lenvatinib in breast cancer as mentioned in Matsui et al. When compared with bevacizumab in breast cancer xenograft models lenvatinib provided better antitumor activity as described by Yano et al. Lenvatinib is approved for use in thyroid cancer. Clinical trials are currently under way evaluating lenvatinib in patients with hepatocellular, lung, and other cancers. Eribulin is a microtubule inhibitor shown to improve OS in breast cancer and with activity in other solid tumors such as NSCLC. Recently data from Study 309 showed an improvement in OS in patients with advanced sarcoma with Eribulin compared with dacarbazine, a standard treatment in sarcoma (data not published yet). We propose a phase II clinical trial of the combination of Eribulin and lenvatinib in breast cancer, non-small cell lung cancer (NSCLC) and sarcoma.

Primary objective will be response rate with secondary objectives toxicity, progression free survival, and overall survival. If the combination is deemed safe future randomized phase II trials will be designed.

2.4 Rationale for patient population

Patients with stage IV cancer will be included in this trial. Data on xenograft models has shown activity of Lenvatinib and recently it has been approved for use in radioiodine resistant thyroid cancer with significantly improved PFS. Furthermore, Eribulin is a microtubule inhibitor which has already shown to improve overall survival in breast cancer, and recently has shown activity in Sarcoma. Given the above

data, we have elected to include stage 4 breast cancer, sarcoma and Non small cell lung cancer patients in our trial.

2.4.1 Micro RNA assay

Our goal is also to quantify serum levels of microRNAs pre- and post-treatment, with the goal of correlating levels with patient response to treatment.

RNA isolation. RNA will be isolated using the mirVanaTM miRNA Isolation Kit (Ambion) and quantified using a Nanodrop spectrophotometer. RNA quality will be determined on an Agilent 2100 Bioanalyzer. miRNA expression profiling will be determined by NGS. We will use the HiSeq 2000 Sequencing System (Illumina) at the GCCRI Genomics Facility to measure miRNA expression profiles. Samples will be barcoded to allow multiplex sequencing and subjected to a second round of Q/C.

Data analysis. Adaptor sequences will be removed and reads of the length ≤ 15 or ≥ 30 are removed as they are not likely to originate from mature miRNAs. Duplicate reads will be removed with the remaining unique reads stored in FASTA format along with the read count. Unique reads will be aligned to the reference human genome (hg19) using the Bowtie short read aligner (0.12.9). Reads mapped to known miRNA loci as defined by miRbase (v21) will be kept for expression profiling. miRNA expression will be derived from counting reads perfectly matching known miRNA loci, normalized to the total number of uniquely mapped reads per sample.

Expected results. Expression profiles of serum miRNAs in 10 responders and 10 non-responders, which can then be compared by t-test to identify differentially expressed miRNAs that correlate with patient response to treatment.

3.0 Objective

The overall purpose of this study is to determine the efficacy and safety of the combination of Eribulin, and Lenvatinib in stage 4 breast, NSCLC and sarcoma.

Primary objective

To determine the overall response rate of the combination of lenvatinib and Eribulin

Secondary objectives

- 1) Determine the safety of Eribulin and lenvatinib
- 2) Define the progression free survival
- 3) Expression profile of MicroRNA

3.1 Selection of Patients

The target population for this study is patients with stage IV breast, NSCLC lung cancers and Sarcoma.

This will be a multi-center trial conducted by Mays Cancer Center. At Mays Cancer Center, patients will be recruited by the clinical team in the Breast Center; lung center and sarcoma center. Potential patients may be referred to the Principal Investigator, [name], at [contact].

Eligibility will be evaluated by the study team according to the following criteria. Eligibility waivers are not permitted. Subjects must meet all of the inclusion and none of the exclusion criteria to be registered to the study. Study treatment may not begin until a subject is registered. Please refer to Section 11 for complete instructions regarding registration procedures.

Inclusion Criteria

- Stage IV breast cancer, stage IV NSCLC, stage IV sarcoma
- ECOG PS 0-2
- Measurable disease
- No more than 4 prior chemotherapeutic regimens for metastatic disease
- Patients must be \geq 18 years.
- Patients may not have received Eribulin or lenvatinib previously
- Patients must have a life expectancy of greater than 12 weeks.
- Patients may have had a prior diagnosis of cancer if it has been $>$ 5 years since their last treatment and are considered free of disease.
- Patients must have normal organ and marrow function as defined below:
 - Leukocytes \geq 3,000/ μ L
 - Absolute neutrophil count \geq 1,500/ μ L
 - Platelets \geq 100,000/ μ L
 - Child Pugh score \leq 10
- Patients must be able to swallow and retain oral medication.
- All patients must have given signed, informed consent prior to registration on study.

Exclusion Criteria

- Women who are pregnant or lactating are not eligible for study treatment.
- Patients who are undergoing concomitant radiotherapy are NOT eligible for participation.
- Patients who are receiving any other investigational agents or concurrent anticancer therapy are NOT eligible for participation. Previous systemic treatment and/or radiation therapy is allowed with a 14 day washout period prior to registration.
- Lesions that have been radiated previously cannot be considered target lesions
- Prior treatment related side effects must have resolved to $<$ Grade 2 severity per Common Terminology Criteria for Adverse Events (CTCAE version 4.03), except alopecia and infertility.
- Patients who are taking any herbal (alternative) medicines are NOT eligible for participation. Patients must be off any such medications by the time of registration.
- Patients with known brain metastases are NOT eligible for participation unless the brain metastases are treated (either with surgical excision, stereotactic radiosurgery or radiotherapy) and have been stable based on the physician's assessment, the patient is asymptomatic and has discontinued corticosteroids if taken for that purpose.
- Patients with any of the following conditions or complications are NOT eligible for participation:
 1. GI tract disease resulting in an inability to take oral medication
 2. Malabsorption syndrome
 3. Require IV alimentation
 4. History of prior surgical procedures affecting absorption
 5. Uncontrolled inflammatory GI disease (e.g., Crohn's, ulcerative colitis).
 6. Hypersensitivity of any of the components of Eribulin or lenvatinib
 7. History of significant neurological (no neuropathy more than grade 2) or psychiatric disorders

8. Significant non neoplastic liver disease (Cirrhosis, active chronic hepatitis)
9. Immunocompromised subjects, including patients with human immunodeficiency virus
10. Significant non neoplastic renal disease
11. Active infection requiring systemic therapy.
12. Significant cardiovascular impairment: history of congestive heart failure greater than New York Heart Association (NYHA) Class II, uncontrolled arterial hypertension, unstable angina, myocardial infarction or stroke within 6 months of the first dose of study drug; or cardiac arrhythmia requiring medical treatment
13. Prolongation of QTc interval to more than 480 milliseconds when electrolyte balance is normal
14. Major surgery within 4 weeks prior to first dose of the study drug.

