4.0 Treatment plan

4.1 Overview

This will be a phase II, non-randomized trial to determine the efficacy and safety of the combination of Eribulin, and lenvatinib in patients with metastatic breast cancer, non-small cell lung cancer and sarcoma. Treatments will be given in cycles of 3 weeks (21 days) and staging scans(CT Scans) will be performed every 2 cycles. Bone scans and MRI brain will be optional. Toxicity assessment will take place after each cycle.

Eribulin will be administered on cycle days 1 and 8; lenvatinib is an orally administered medication which will be given daily throughout each cycle (on cycle 1 lenvatinib will be started on day 2). On days when both drugs are administered, Eribulin will be administered immediately prior to lenvatinib.

Patients will be followed after treatment discontinuation until disease recurrence or death. An evaluable patient for toxicity is any patient who has received at least 1 dose of any of the study drugs. An evaluable patient for efficacy is any patient who has received at least 2 cycles of therapy.

There will be a safety run-in phase. Ten patients will receive lenvatinib at 20 mg daily and Eribulin at 1.4 mg/m² day 1 and day 8 of a 21 day cycle. Eribulin will be given on day 1 and lenvatinib at 20 mg daily will be started on day 2. After completion of 1 cycle of therapy for the first 10 patients the PI will have a teleconference with the medical team at EISAI and decide whether to continue at the same dose or increase the dose to 24 mg daily of lenvatinib and Eribulin at 1.4 mg/m² day 1 and day 8 of a 21 day cycle.

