4.2 Study Drug Administration

Eribulin

Eribulin will be administered intravenously (IV) on days 1 and 8 of each cycle at a dose of 1.4 mg/m² over a 2-5 minute time period; on cycle day 1 in the Phase II portion of the trial; this will be immediately prior to Lenvatinib administration. Eribulin will be administered to the patient in the clinic (for drug preparation instructions, see section 7.0). Each cycle will last 21 (+/- 3) days. Laboratory tests will be performed within 2 days prior to days 1 and 8 of all cycles to assess toxicity and confirm that it is safe to proceed with treatment (see Section 7.0 for a complete listing of assessments). The dose of Eribulin will be calculated based on the BSA at study entry and *should only be recalculated if there is >10% change in body weight from baseline*. The actual body weight will be used for these calculations.

Lenvatinib

Lenvatinib will be self-administered by patients orally once a day during the study period. Patients will self-administer lenvatinib at home, except on study visit days. On these visit days, patients should take lenvatinib after chemotherapy is administered. Patients will be instructed to take each dose orally once daily, with or without food, starting on day 2 of cycle 1. The capsules should be swallowed whole without chewing, dissolving, or opening them. Patients should be instructed to take their dose of study drug at the same time each day. If the usual dosing time is missed, the patient should take the dose that day as soon as they remember as long as this is within 12 hours of the usual time the patient takes the dose. If it has been over 12 hours then this will be considered a missed dose. Patients should not make up missed or vomited doses; dosing should resume on the next calendar day unless otherwise instructed. Patients will be given a medication diary to record all doses taken, missed/skipped, or vomited. This diary will be reviewed with study personnel prior to dispensing medication for the next cycle.

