4.3 Supportive Care Guidelines

Supportive therapy for neutropenia:

If grade 3 or 4 neutropenia develops (ANC<1000/uL), G-CSF (Neupogen) can be administered, at the discretion of the treating investigator, until resolution of neutropenia. Neulasta (PEG-filgrastim) 6mg SC for 1 dose is recommended. If Neulasta is given, chemotherapy cannot be administered within 14 days. Neupogen can also be given at the discretion of the treating investigator. NOTE: Neupogen can be given any time before or after chemo. HOWEVER, Neulasta cannot be given within 14 days of chemotherapy.

Supportive therapy for neuropathy

Gabapentin or similar medications can be given at the discretion of the treating physician per institutional practice.

Dose Delays & Dose Modifications

Toxicities will be graded using NCI CTCAE version 4.03 (see Appendices). Dose delays and modification of lenvatinib and Eribulin are summarized below (for post-DLT period in phase II patients only). Individual patient dose reductions are also provided in separate tables.

Dose Delay & Modification for Eribulin and Lenvatinib

Toxicity	Adverse event	Dose Reduction/Delay	
		Eribulin	Lenvatinib
Hematologic toxicity attributed to any or all treatment	Platelets 75000-99999/mm ³ within 24 hrs prior to scheduled therapy	If Day 1: Hold until recovery of platelets >100,000/mm ³ . Resume at the same level after recovery If Day 8: No intervention	No dose modification necessary
	ANC <1000/mm ³ or Platelets 25000-74999/mm ³ within 24 hrs prior to scheduled therapy	If Day 1: Hold until recovery to ANC >1000/mm ³ and Platelets 100000/mm ³ . Resume at same level after recovery If Day 8: Hold until recovery to ANC >1000/mm ³ and Platelets 75000/mm ³ . Resume at same level after recovery	Hold until recovery to ANC >500/mm ³ and platelets more than 25000, Resume at same level after recovery.
	Platelets <25000/mm ³ or Platelets 25000-50000/mm ³ complicated by bleeding, easy bruising, petechiae, or requiring platelet transfusion	If Day 1: Hold until recovery to Platelets 100000/mm ³ . Resume at same level after recovery If Day 8: Hold until recovery to Platelets 75000/mm ³ . Resume at same level after recovery	Hold until recovery of Platelets 25000/mm ³ . Resume at current dose level.

	Prolonged neutropenia (ANC<500/mm ³ for >7 days)	Hold until recovery to ANC>1000/mm ³ . Resume at one dose level below current dose level	Hold until recovery to ANC>500/mm ³ . Resume at same level dose.

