	Febrile neutropenia (ANC <1000/mm ³ with temperature of >38.5°C)	Hold until recovery to ANC>1000/mm ³ . Resume at one dose level below current dose level	Hold until recovery to ANC>1000/mm ³ . Resume at same dose level
	Anemia	No reduction or delay	No reduction of delay
Hepatic toxicity	Grade 4 AST, ALT or Total Bilirubin Child Pugh Score	For patients with known liver dysfunction and Child Pugh score A, Eribulin should be started at a dose of 1.1mg/m ² . For patients with known liver dysfunction and Child Pugh score B, Eribulin should be started at a dose of 0.7mg/m ² . Eribulin should not be administered in patients with Child Pugh score C. If during treatment there is grade 3,4 liver toxicity then dose reduce by 1 dose level.	Hold until recovery to Grade 1 or baseline. Resume at reduced dose of 20 mg po daily if first occurrence, reduce to 14 mg po daily on second occurrence and 10 mg po daily on third occurrence.

Peripheral neuropathy	Grade 3 or 4	Hold until recover to \leq grade 2. Reduce dose by one dose level. If neuropathy fails to recover to grade 2 within 3 weeks, Eribulin should be discontinued.	No modifications necessary
Non-hematologic toxicity grade 3 or 4 attributed to any or all treatment (except for neuropathy)	Grade 3 or 4 nausea/vomiting despite optimal antiemetic treatment	Hold until nausea/vomiting have resolved to \leq grade 1. Resume at same dose level	Hold until nausea/vomiting have resolved to \leq grade 1. Resume at same dose.
	>Grade 2 stomatitis	Hold until stomatitis has resolved to \leq grade 1. Resume at one dose level below current dose level	Hold until recovery to \leq grade 1. Resume at the same dose level
Hypertension	Grade 3 Hypertension Or life threatening Hypertension	No dose modification necessary.	Withhold lenvatinib for Grade 3 hypertension that persists despite optimal antihypertensive therapy; resume at one dose level below current dose level. Discontinue for life threatening hypertension.
Cardiac dysfunction or Hemorrhage.	Grade 3 or Grade 4 events	No dose modification necessary	Withhold lenvatinib for development of Grade 3 event until improved to Grade 0 or 1 or baseline. Either resume at a reduced dose or discontinue lenvatinib depending on the severity and persistence of the adverse event.

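### Eribulin's hepatic starting doses and its class C bar appear only in a section 4.3 table whose scope label leaves their use at the first dose unclear, while the other dosing text gives 1.4 mg/m2 without exception

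*Combined protocol and SAP*

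**What the plan says.** Eligibility (section 3.1) sets blood-count limits and one liver limit, a Child-Pugh score of 10 or less, under the line "Patients must have normal organ and marrow function as defined below". The same section adds "Eligibility waivers are not permitted". The liver exclusion covers "Significant non neoplastic liver disease (Cirrhosis, active chronic hepatitis)".

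The hepatic row of the table in section 4.3 gives starting doses of eribulin for patients with known liver dysfunction: 1.1 mg/m2 for Child-Pugh A, and for B "For patients with known liver dysfunction and Child Pugh score B, Eribulin should be started at a dose of" 0.7 mg/m2. It continues: "Eribulin should not be administered in patients with Child Pugh score C". The sentence introducing the table reads "Dose delays and modification of lenvatinib and Eribulin are summarized below (for post-DLT period in phase II patients only)".

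Appendix III makes the first cycle the DLT period. Appendix IV ties the 21-day DLT data submissions to phase I patients only, and the data submission table in Appendix V labels its DLT column the same way.

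The other dosing text gives one dose. Section 4.1: "Ten patients will receive lenvatinib at 20 mg daily and Eribulin at 1.4" mg/m2. Section 4.2: "Eribulin will be administered intravenously (IV) on days 1 and 8 of each cycle at a dose of 1.4" mg/m2. The synopsis and sections 7.1 and 8.1.1 repeat 1.4 mg/m2. Table 1 in section 4.3, whose lead-in says that it includes the starting dose, has 1.4 at level 0. None of these places mentions a hepatic exception or points to the hepatic row.

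**The concern.** A starting-dose rule has effect only at the first dose. Here it sits in a table for delays and modifications whose label, taken literally, begins after cycle 1 and leaves out the run-in patients. Staff who prepare eribulin from section 4.2, which sends them to section 7.0 for preparation, would find 1.4 mg/m2 in both places and would not meet the hepatic rule.

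Affected patients can enter. The liver exclusion is limited to non-neoplastic disease, so it does not remove dysfunction caused by liver metastases, and everyone in the trial has stage IV cancer. The plan itself expects such patients, since it writes doses for classes A and B. At stake is a first cycle of a cytotoxic drug above the dose that the protocol sets for impaired liver function.

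A secondary matter is that eligibility uses a number and the dosing rule uses class letters. The protocol does not say which letter a score of 10 carries.

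**Working it through.** The plan states no figure on this point. The check is a comparison of texts, followed by simple arithmetic on the doses.

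**Where the rule applies**

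- Section 4.3, hepatic row: fixes the dose at which eribulin begins, so it must act on cycle 1 day 1.
- Section 4.3, introduction to the table: limits the content to the post-DLT period in phase II.
- Appendix III: the DLT period is cycle 1, and any enrolled and treated patient should be evaluated for DLT. With this definition, the label excludes every patient's first dose and all run-in patients.
- Appendices IV and V: DLT-period data are required only of phase I patients, the term that section 11.1.2 uses for the run-in. With this usage, the label can mean the stage after the run-in, and phase II patients are covered from day 1. Run-in patients are still outside the label.

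Both readings have textual support, so the scope is unclear.

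**Size if a site doses at 1.4 mg/m2**

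Inputs: standard dose 1.4 mg/m2 (sections 4.1, 4.2 and 7.1; Table 1 level 0); hepatic starting doses 1.1 and 0.7 mg/m2 (section 4.3 table); two doses in cycle 1, on days 1 and 8 (section 4.2); Table 1 levels 0 = 1.4, -1 = 1.1, -2 = 0.7.

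Ratio = standard dose / hepatic starting dose. Cycle 1 total = 2 x dose.

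- Class A: 1.4 / 1.1 = 1.27. Cycle 1 total 2 x 1.4 = 2.8 against 2 x 1.1 = 2.2 mg/m2, an excess of 0.6. The start is one Table 1 level too high.
- Class B: 1.4 / 0.7 = 2.0. Cycle 1 total 2.8 against 2 x 0.7 = 1.4 mg/m2, an excess of 1.4. The start is two Table 1 levels too high.

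**Score and class**

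The remaining mentions of Child-Pugh are in the lenvatinib label (Appendix I). They pair letters with mild, moderate or severe impairment and give no points. The start of class C is therefore an assumption:

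- If class C starts at 10, one eligible score (10) is barred from eribulin.
- If class C starts at 11, no eligible score is barred.

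**The case against.** The label speaks of delays and modifications, and the hepatic row is plainly a starting rule. A reading that leaves the rule with nothing to govern is the least natural one, and a specific exception ordinarily prevails over a general dose. Table 1 lists levels for toxicity, so its level 0 is weak evidence of a competing starting dose. Child-Pugh is a named scale, and the protocol uses ECOG and NYHA without defining them either. There are also safeguards: cirrhosis and active chronic hepatitis are excluded, the principal investigator reviews registrations, and laboratory tests precede days 1 and 8.

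Much of this stands. Use of the hepatic rule at entry is probably what the sponsor intends. A reader might infer that the label and the rule flatly contradict each other; Appendices IV and V do not allow that conclusion. The missing link between number and letter is mostly absent detail on a known scale.

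The objection does not repair the dosing path. Sections 4.2 and 7.1 still give 1.4 mg/m2 without a pointer, and one reading of the label still switches the rule off in cycle 1. The registration steps confirm eligibility; nothing says that they set the eribulin dose. For phase II, section 11.1.3 does not list laboratory results among the items to submit, whereas section 11.1.2 asks affiliate sites for them in the run-in. Relying on inferred intent is a poor safeguard in a multi-center trial.

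**Conclusion.** The point holds as a minor patient-safety matter of placement and scope. If a site doses from section 4.1, 4.2, 7.1 or Table 1, or reads the label literally, a class A patient starts at 1.27 times and a class B patient at 2.0 times the protocol's own hepatic dose. These are ratios of doses in the text, conditional on the hepatic row being missed or set aside. They do not estimate harm.

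The documents give no count of affected patients; few are likely. The note to Table 2 in section 4.3 records that the lenvatinib dose decision from the first ten patients has been made, so a change now mainly protects later patients.

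A reader might also infer that the protocol admits class C patients and then forbids them eribulin. The documents do not support this, because they never say where class C begins. That part matters only if a score of 10 belongs to class C. Even then, section 4.3 bars the drug, so actual dosing of a recognised class C patient is unlikely.

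**What to change.** - In section 4.2, state the hepatic starting doses (A 1.1 mg/m2, B 0.7 mg/m2) and the class C bar, and say that they apply to all patients from cycle 1 day 1.
- In section 4.3, exempt the hepatic starting-dose row from the scope label of the table.
- In section 7.1 and at Table 1, refer to the rule in section 4.2.
- Secondary: in section 3.1, express the liver limit in the same class terms as the dosing rule and exclude class C, so that no eligible patient is barred from eribulin.

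The cost is a small wording amendment. A few patients may no longer be eligible if a score of 10 proves to be class C. Patients started at a reduced dose do not test eribulin at 1.4 mg/m2, which should be kept in mind when tolerability is described. Sample size, endpoint and decision rule are unchanged.

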¹¹Lenvatinib may cause proteinuria. Patients with 2+ or greater urine dipstick reading should undergo further assessment with a 24-hour urine collection. If 24hr urine protein ≥ 2 g then suspend lenvatinib until it decreases to <2 g and dose reduce by one dose level. If nephrotic syndrome then permanently discontinue lenvatinib.

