7.2 Lenvatinib

Other names

Lenvima

Classification

LENVIMA, a kinase inhibitor, is the mesylate salt of lenvatinib. Its chemical name is 4-[3-chloro-4-(*N*¹-cyclopropylureido)phenoxy]-7-methoxyquinoline-6-carboxamidemethanesulfonate.

Mode of action

Lenvatinib is a receptor tyrosine kinase (RTK) inhibitor that inhibits the kinase activities of vascular endothelial growth factor (VEGF) receptors VEGFR1 (FLT1), VEGFR2 (KDR), and VEGFR3 (FLT4). Lenvatinib also inhibits other RTKs that have been implicated in pathogenic angiogenesis, tumor growth, and cancer progression in addition to their normal cellular functions, including fibroblast growth factor (FGF) receptors FGFR1, 2, 3, and 4; the platelet derived growth factor receptor alpha (PDGFR α), KIT, and RET.

Storage and Stability

Store at 25°C (77°F); excursions permitted to 15–30°C (59–86°F)

Protocol dose

Lenvatinib is administered at a dose of 20 mg orally.

Preparation

LENVIMA 4 mg capsules are supplied as hard hyperomellose capsules with yellowish-red body and yellowish-red cap, marked in black ink with “€” on the cap and “LENV 4 mg” on the body.

LENVIMA 10 mg capsules are supplied as hard hyperomellose capsules with yellow body and yellowish-red cap, marked in black ink with “€” on the cap and “LENV 10 mg” on the body.

Protocol administration

Lenvatinib is administered orally 20 mg po daily. It will be administered immediately after the Eribulin administration.

Incompatibilities

None

Availability

Lenvima will be supplied by Eisai, Inc in cards containing 10 mg and 4 mg capsules. To order drug, please contact EISAI IIS Department at [contact] or [contact]

Side effects

Detailed information regarding side effects and rates of adverse events of lenvatinib can be found in the package insert. Some of the most common side effects include:

Hypertension

The median time to onset of new or worsening hypertension was 16 days for LENVIMA-treated patients. The incidence of Grade 3 hypertension was 44% as compared to 4% for placebo, and the incidence of Grade 4 hypertension was less than 1% in LENVIMA-treated patients and none in the placebo group.

Cardiac dysfunction

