The recommended dose of LENVIMA is 14 mg taken orally once daily in patients with severe renal impairment (creatinine clearance [CLcr] less than 30 mL/min calculated by the Cockcroft-Gault equation) or severe hepatic impairment (Child-Pugh C).

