5.5 Proteinuria

In Study 1, proteinuria was reported in 34% of LENVIMA-treated patients and 3% of patients in the placebo group [*see Adverse Reactions (6.1)*]. The incidence of Grade 3 proteinuria in LENVIMA-treated patients was 11% compared to none in the placebo group.

Monitor for proteinuria before initiation of, and periodically throughout treatment. If urine dipstick proteinuria greater than or equal to 2+ is detected, obtain a 24 hour urine protein. Withhold LENVIMA for ≥ 2 grams of proteinuria/24 hours and resume at a reduced dose when proteinuria is < 2 gm/24 hours. Discontinue LENVIMA for nephrotic syndrome [*see Dosage and Administration (2.2)*].

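### The proteinuria row in section 4.3 reverses the lenvatinib hold and restart limits; a smaller gap is that section 3.1 sets no renal value for entry

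*Combined protocol and SAP*

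**What the plan says.** **Proteinuria on treatment.** In the section 4.3 table, the lenvatinib cell of the proteinuria row holds the drug at 24-hour protein of 2 g or less. It restarts one dose level lower once protein is above 2 g, and stops the drug for nephrotic syndrome. Section 4.3 limits the table to phase II patients after the DLT period, which Appendix III sets as the first cycle.

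Footnote 11 in section 6.0 sits on the urinalysis row, which is marked at screening and every two cycles. It reads: "Patients with 2+ or greater urine dipstick reading should undergo further assessment with a 24-hour urine collection". At a 24-hour result of 2 g or more, the instruction is "then suspend lenvatinib until it decreases to" less than 2 g, with a reduction of one level. The label in Appendix I (section 5.5) sets the hold at 2 or more "grams of proteinuria/24 hours and resume at a reduced dose when proteinuria is" below 2 g; its section 2.2 repeats this.

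**Renal function at entry.** Section 3.1 states "Patients must have normal organ and marrow function as defined below" and then gives limits for leukocytes, neutrophils, platelets and Child-Pugh. Exclusion 10 is "Significant non neoplastic renal disease". The starting dose is the same for everyone: section 4.1 has "lenvatinib at 20 mg daily will be started on day 2" and section 7.2 has "Lenvatinib is administered at a dose of 20 mg orally". Only Appendix I adjusts for renal function: "The recommended dose of LENVIMA is 14 mg taken orally once daily in patients with severe renal impairment", defined there as creatinine clearance below 30 mL/min.

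**The concern.** The protocol gives two opposite instructions for a known lenvatinib toxicity. Staff working from the section 4.3 table would keep dosing a patient whose protein loss is above the level at which footnote 11 stops the drug. They would also restart a held patient because protein loss had risen. In the other direction, a patient under 2 g would be taken off drug with no route back unless proteinuria worsened. Section 4.7 then removes a patient whose treatment is held for two consecutive cycles.

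The entry gap matters less. Hepatic impairment has a stated eribulin starting dose in section 4.3, but the protocol body has no renal starting dose for either drug, and no renal result is tied to eligibility. At stake is individual patient safety, not the trial's inference.

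**Working it through.** **1. The three proteinuria rules side by side**

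| 24-hour protein | Section 4.3 row, on drug | Footnote 11 and label, on drug | Section 4.3 row, on hold | Footnote 11 and label, on hold |
|---|---|---|---|---|
| below 2 g | withhold | continue | stay off | restart one level lower |
| exactly 2 g | withhold | withhold | stay off | stay off |
| above 2 g | continue | withhold | restart one level lower | stay off |

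(The label says a reduced dose, where the protocol says one level.) The rules agree only at exactly 2 g. Read literally, the row would also hold the drug in a patient with no proteinuria at all, so it cannot be what was intended. All three sources stop the drug for nephrotic syndrome.

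**2. How often the row would be consulted.** The documents give no rate for this combination. In the lenvatinib studies they cite, Grade 3 or higher proteinuria ranges from 2% (medullary thyroid phase II) through 4% (melanoma phase II) and 11% (label study) to 15% (phase 1 with everolimus). If that range carried over to 30 phase II patients, 30 × 0.02 = 0.6 to 30 × 0.15 = 4.5 would be affected. Doses, tumours and partner drugs differ, and these grades are not the 2 g cut, so this is only an order of magnitude.

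**3. Entry gap: starting dose against the label figure.** Inputs are the protocol start of 20 mg (4.1, 7.2), the label dose below 30 mL/min of 14 mg, and the usual label dose of 24 mg (Appendix I).

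- Excess over the label figure: 20 − 14 = 6 mg; 20/14 = 1.43.
- Label's own reduction: (24 − 14)/24 = 10/24 = 42%.
- Protocol's reduction of the starting dose: 0.

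**4. Number of such patients.** None is given. Under an assumed prevalence of 0.5% to 5%, 30 × 0.005 = 0.15 to 30 × 0.05 = 1.5 patients would be expected among 30. That is before exclusion 10 and the prior-toxicity rule remove most of them.

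**5. Design figures.** The section 8.1.2 table reproduces. With N = 30 and rejection at 10 or more responses, the exact binomial tail is 0.0611 at p = 0.2 and 0.8237 at p = 0.4. Neither part of this point enters that calculation.

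**The case against.** **The row may be a typing or extraction fault.** Its text is visibly damaged: there is a stray item number, and the event cell names values both above and below 2 g. Footnote 11 and both label sections give the right direction, and a clinician would probably follow them. What stands is that both inequalities in the row are reversed together, which one misread symbol does not explain. The posted PDF should be checked first. If it reads as here, the error is in the operative dosing table.

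**The entry gap is narrow.** This is largely right:

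- Non-neoplastic clearance below 30 mL/min would hardly escape exclusion 10.
- Prior-treatment effects must be below Grade 2.
- Chemistry is repeated on day 1, before lenvatinib starts on day 2.
- Footnote 11 sits on a row that includes screening, so heavy proteinuria should be caught before the first dose, although its wording is for a patient already on drug.

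What remains is mainly tumour-related severe impairment. The 14 mg dose is also not absent from the document: Appendix I states it, but sections 4.2 and 7.2 do not carry it over.

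**Excluding these patients goes further than the label.** The label doses them at 14 mg and lists no contraindications. That objection stands, so a 14 mg start is offered first in the fix.

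**Conclusion.** The section 4.3 proteinuria row is wrong as written. It contradicts footnote 11 and the label at every value except exactly 2 g, and it governs phase II patients after cycle 1. This conclusion rests on the extracted text matching the PDF.

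The missing renal value in section 3.1 is a minor, secondary gap. It leaves a possible 6 mg difference from the label figure in a rare patient whose frequency the documents do not give.

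A reader might infer more, and the documents do not support it:

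- **Overexposure at 20 mg.** Appendix I (12.3) reports similar AUC in renal impairment after a single 24 mg dose. The ratio of 1.43 measures departure from label wording, not shown exposure or harm, and the label figure comes from thyroid cancer.
- **Entry wide open to renal impairment.** The safeguards listed under the objection cover most cases.
- **Harm to the primary analysis.** Nothing here changes the response rate, alpha or power.

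**What to change.** 1. **Section 4.3, proteinuria row:** withhold lenvatinib at 24-hour protein of 2 g or more, resume one dose level lower when below 2 g, and discontinue for nephrotic syndrome. Simplify the event cell to 2 g or more. This costs one table row.
2. **Renal starting rule:** carry the label rule into section 4.2 (start at 14 mg when creatinine clearance is below 30 mL/min), or add a minimum clearance of 30 mL/min to the list in section 3.1. A 14 mg start is already dose level −1, the lowest in Table 2 of section 4.3. That option therefore also needs a statement of what follows: 10 mg, as in the label and the hepatic row, or discontinuation. The clearance limit is simpler, but makes a few patients ineligible.
3. **Footnote 11:** state that it applies to the screening urinalysis and must be resolved before the first lenvatinib dose.

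The cost is amended wording and, for item 2, an updated eligibility checklist if the clearance limit is chosen. The chemistry panel (assumed to include creatinine) and urinalysis are already done at screening, and footnote 11 already calls for the 24-hour collection. Section 4.3 records that the first ten patients have been assessed, so the change helps only patients still to be enrolled or still on treatment.
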